## 10.8 Multiplicity

There will be no multiplicity control in this study.

### 10.9 Sample Size and Power Calculations

For the planning purpose, it is assumed that true objective response rates of <1% for MSS CRC and 5% for PDL1-refractory NCSLC and advanced prostate are not considered clinically meaningful, whereas true objective response rates of 16% for MSS CRC and 20% for PDL1-refractory NCSLC and advanced prostate or higher are. With 20 participants in each tumor type of each arm under the 2-stage adaptive design, the probability that the objective response rate of each tumor type is claimed clinical meaningful is less than 8% when the true response rate is not clinically meaningful and more than 75% when the true response rate is clinically meaningful. The total sample size is 60 participants per arm (20 per each tumor type in an arm). No formal hypothesis testing will be conducted. Table 8 provides the probability that the objective response rate of each tumor type is claimed clinical meaningful under different true ORR. Table 9 shows the hypothetical ORR estimates and the CI (Clopper-Pearson interval) based on sample size of 20 per tumor type. Due to a small sample size, even an observed response rate as high as 30% (6 out of 20) could be coming from a true signal as low as 14%. A higher observed responses rate such as 8 out of 20 would be more indicative of a true response rate above 20%.

Probability That ORR is Claimed as Clinical Interest With 20 Participants in Each Table 8 Tumor Type of Each Arm

Tumor Type	ORR as clinical meaningful	True ORR	Minimum Responses that ORR is claimed as clinical meaningful	Probability that ORR is claimed as clinical meaningful
CRC	16%	1%	2	1%
		16%	2	77%
NSCLC,				
Prostate	20%	5%	3	7%
		20%	3	76%

The CI of the True ORR Under Different Hypothetical Number of Observed Response Scenarios With 20 Participants in Each Tumor Type of Each Arm

Hypothetical number of responses (CR or PR)	ORR	90% CI of ORR	80% CI of ORR
2	10%	(1.8%, 28.3%)	(2.7%, 24.5%)
3	15%	(4.2%, 34.4%)	(5.6%, 30.4%)
4	20%	(7.1%, 40.1%)	(9.0%, 36.1%)
5	25%	(10.4%, 45.6%)	(12.7%, 41.5%)
6	30%	(14.0%, 50.8%)	(16.6%, 46.7%)
7	35%	(17.7%, 55.8%)	(20.7%, 51.8%)
8	40%	(21.7%, 60.6%)	(24.9%, 56.7%)

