# Treatment Crouns and Duration.

eatment Groups and Duration:										
Treatment Groups	Participants will be stratified by tumor type and randomized 1:1 to either of 2 dose level arms: Arm A will receive 30 mg navarixin orally QD + pembrolizumab 200 mg IV Q3W; Arm B will receive 100 mg navarixin orally QD + pembrolizumab 200 mg IV Q3W.									
	In Stage 1 of the study, 30 participants will be randomized to each arm. In Stage 2, barring early termination of the arm, 30 additional participants will be randomized to each arm.									
Duration of Participation	Each participant will participate in the study from the time the participant signs the informed consent form (ICF) through the final protocol-specified contact.									
	After a screening phase of up to 28 days, each participant will be assigned to receive study treatment until disease progression is radiographically documented and, when clinically appropriate, confirmed by the site per modified Response Evaluation Criteria in Solid Tumors 1.1 for immune-based therapeutics (iRECIST), unacceptable adverse event(s) (AEs), intercurrent illness that prevents further administration of treatment, Investigator's decision to withdraw the participant, noncompliance with study treatment or procedure requirements, administrative reasons requiring cessation of treatment, or until the participant has received 35 administrations (approximately 2 years) of combination treatment with navarixin and pembrolizumab. Monotherapy treatment with pembrolizumab will be allowed if navarixin treatment is withheld for ANC or febrile neutropenia.									
	After the end of treatment, each participant will be followed for the occurrence of AEs and spontaneously reported pregnancy as described under Section 9.3.									
	Participants who discontinue for reasons other than radiographic disease progression will have post-treatment follow-up imaging for disease status until disease progression is documented radiographically per RECIST 1.1 and, when clinically appropriate, confirmed by the site per iRECIST, initiating a non-study cancer treatment, withdrawing consent, becoming lost to follow-up or the end of the study. All participants will be followed by telephone									
	for overall survival until death, participant withdrawal of consent, becoming lost to follow-up or the end of the study.									

**Protocol/Amendment No.:** 034-01

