The overall design is an adaptive 2-stage design. In each arm, up to 30 participants will be enrolled in the first stage, and up to 30 participants in the second stage. In the first stage, 30 participants (with 10 per tumor type) will be enrolled in each arm (dose level). When all participants in a given arm with a given tumor type complete the first on-treatment scan at 9 weeks or when clinically indicated (see Section 9.2.1.2), a futility analysis will be conducted to determine whether that tumor type and arm will progress to Stage 2. If a tumor type passes the futility analysis (see Section 5.1.4) in Stage 1, at least 10 participants will be enrolled with that tumor type in the second stage.

Initial enrollment in each dose arm will be staggered. The first 3 participants in dose Arm A or dose Arm B will be enrolled no more frequently than 1 participant per week, to allow for peripheral neutrophil assessment between participants. Peripheral neutrophil assessment (ANC) will occur at baseline, Day 3, and Day 8 during the first cycle for all participants. Decreased ANC counts typically return to normal in 48-96 hours following dosing cessation. Standard support for oncology patients with low ANC will be considered as appropriate. See dose reduction algorithm (Section 7.2.1) for more information.

Specific procedures to be performed during the study, as well as their prescribed times and associated visit windows, are outlined in the Study SoA - Section 2. Details of each procedure are provided in Section 9 – Study Assessments and Procedures.

04W5XD

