#### **Futility Analysis** 5.1.4

An interim futility analysis for efficacy will be performed after the first 10 participants for each tumor type have at least 1 post-baseline scan assessment in each dose arm in Stage 1. If one or more responses (confirmed or unconfirmed) are observed for a tumor type in an arm (i.e.  $\geq$ 10% response rate), this tumor type may be expanded to enroll at least additional 10 participants in Stage 2, for a maximum enrollment of 60 participants in this arm across 3 tumor types. Otherwise, this tumor type may be stopped early for futility.

If the decision is made to expand a tumor type in dose Arm A to Stage 2, this tumor type in dose Arm B may be expanded to Stage 2 as well, irrespective of the number of responses as long as it has passed the safety evaluation. While the decision rule is mainly based on confirmed and unconfirmed responses, the totality of data will also be taken into account.

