#### **Number of Participants** 5.2

Greater than or equal to 120 participants will be randomized in order to achieve 120 evaluable participants as per Section 10. If no efficacy is noted in any tumor types the total number may be as low as 60.

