#### 10.7 Interim Analyses

There is one planned interim safety analysis and one planned interim futility analysis in this trial.

An interim safety analysis is planned for each arm after the first 10 participants across tumor types have finished at least one cycle of therapy in a given arm. If no more than 3 participants in the first 10 participants have experienced DTLs during the first cycle in a given arm, this arm may be expanded by enrolling 20 additional participants to complete Stage 1. Otherwise, this arm may be terminated due to safety concern.

An interim futility analysis is planned for each tumor type in each arm after the first 10 participants in each tumor type have at least 1 post-baseline scan assessment. If 1 or more

responses (ie,  $\geq 10\%$  response rate) are observed in a tumor type within an arm, this tumor type may be expanded to enroll at least 10 additional participants in Stage 2. Otherwise, this tumor type may be stopped early for futility. If the true response rate is 16%, there is an 82% chance to continue the study at the futility evaluation. If the true response rate is 20%, there is an 89% chance to continue the study at the futility evaluation.

Additional interim analysis may be conducted to enable future trial planning at the Sponsor's discretion and data will be examined on a continuous basis to allow for timely decisions.

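### Table 8's claim counts are right at 20 per tumor type and arm, but Stage 2 can take a type to 21–40 and the plan gives no count for those sizes; for NSCLC and CRPC the one stated count of 3 exceeds the 8% bound from n=22.

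*Combined protocol and SAP*

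**What the plan says.** Section 10.9 and Table 8 give a minimum of 2 responses for MSS CRC and 3 for NSCLC and prostate, both for 20 participants per tumor type and arm. The text introduces the bounds with "With 20 participants in each tumor type of each arm under the 2-stage adaptive design, the probability that the objective response rate" and totals 60 per arm, 20 per type.

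The enrolment sections are looser:

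- Section 5.1: for a type that passes futility, "at least 10 participants will be enrolled with that tumor type in the second stage". The same section caps Stage 2 at 30 per arm.
- Section 5.1.4: a type with at least one response in its first 10 "may be expanded to enroll at least additional 10 participants in Stage 2, for a maximum enrollment of 60 participants in this arm" across the three types. Figure 1 also shows 10 or more per cleared type.
- Section 10.7: the "type may be expanded to enroll at least 10 additional participants in Stage 2".
- Synopsis, Treatment Groups and Duration: "In Stage 2, barring early termination of the arm, 30 additional participants will be randomized to each arm". The exception is for stopping an arm, whereas futility stops a tumor type.
- Section 5.2: "Greater than or equal to 120 participants will be randomized in order to achieve 120 evaluable" participants, or as few as 60 if no type shows efficacy. Intermediate outcomes are not described. The synopsis gives approximately 120.

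Section 5.1.4 adds that when a type is expanded in Arm A, the same type in "dose Arm B may be expanded to Stage 2 as well, irrespective of the number of responses", provided that it has passed the safety evaluation.

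**The concern.** If all three types clear in an arm, the 30 Stage 2 places and the minimum of 10 each force n=20, and Table 8 applies. If two clear, one can reach n=30, and an even split gives 25 each. If only one clears, it can reach n=40. The plan does not say how freed places are used or what count applies above 20.

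The trial is open-label, and under Section 10.7 "data will be examined on a continuous basis to allow for timely decisions". A count not fixed in advance could therefore be settled after responses are known. Section 5.4.1.1 says that ORR will be used for decision making, so the claim rule has consequences even without a formal test. The opening of Section 10 requires an amendment if methods for primary objectives change, but that does not supply a count where none was set.

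**Working it through.** **Inputs.** Stage 1 n=10 per type and arm; continue if at least 1 responds (5.1.4, 10.7). Uninteresting and target ORR: 1% and 16% for CRC, 5% and 20% for NSCLC/CRPC; counts 2 and 3; bounds <8% and >75% (10.9). Total n per type: 20 to 40 (10 in Stage 1, plus 10 to 30 under the Stage 2 cap).

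**Formula, with the futility rule.** P(claim) = Σ over x=1..10 of P(X1=x) × P(X2 ≥ r−x), where X1 ~ Bin(10, p), X2 ~ Bin(n−10, p) and r is the count. Without the futility rule, P(claim) = P(Bin(n, p) ≥ r). The second form describes an Arm B type expanded whatever its own responses.

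**Reproducing Table 8 (n=20).** For NSCLC/CRPC at 5% with r=3: 0.3151×0.0861 + 0.0746×0.4013 + 0.0115 = 0.0686, or 6.9% (stated 7%). At 20%: 75.9% (stated 76%). For CRC with r=2: 1.3% and 76.7% (stated 1% and 77%). Table 8 therefore uses the futility rule and is correct.

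**NSCLC/CRPC above n=20.** Each cell gives the value with / without the futility rule.

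| n | Count | Claim at ORR 5% | Claim at ORR 20% |
|---|---|---|---|
| 20 | 3 | 6.9% / 7.5% | 75.9% / 79.4% |
| 21 | 3 | 7.6% / 8.5% | 78.0% / 82.1% |
| 21 | 4 | 1.8% / 1.9% | 61.2% / 63.0% |
| 22 | 3 | 8.3% / 9.5% | 79.8% / 84.6% |
| 22 | 4 | 2.1% / 2.2% | 64.6% / 66.8% |
| 23 | 3 | 9.1% / 10.5% | 81.3% / 86.7% |
| 23 | 4 | 2.4% / 2.6% | 67.6% / 70.3% |
| 24 | 3 | 9.8% / 11.6% | 82.6% / 88.5% |
| 24 | 4 | 2.7% / 3.0% | 70.4% / 73.6% |
| 25 | 3 | 10.5% / 12.7% | 83.7% / 90.2% |
| 25 | 4 | 3.1% / 3.4% | 72.8% / 76.6% |
| 30 | 3 | 14.3% / 18.8% | 87.1% / 95.6% |
| 30 | 4 | 5.1% / 6.1% | 81.4% / 87.7% |
| 40 | 3 | 21.1% / 32.3% | 88.9% / 99.2% |
| 40 | 5 | 3.9% / 4.8% | 84.4% / 92.4% |

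Both probabilities fall as the count rises. So where 3 exceeds 8% and 4 falls short of 75%, no count meets both bounds. That holds at n=22, 23 and 24 in both calculations. At n=21 a count of 3 works with the futility rule and no count works without it. At n=25 the reverse is true: a count of 4 works only without the rule. From n=26 a count that meets both bounds exists in both calculations, although n=26 with a count of 4 passes only just with the rule (75.001%).

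**CRC.** With the futility rule, a count of 2 gives 1.3–2.8% at ORR 1% and 77–82% at ORR 16% for every n from 20 to 40.

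**How often n>20 is permitted in an arm.** Each type clears with probability 1−(1−p)^10. Assuming independence, the futility rule as written and no carry-over to Arm B, exactly two types clear with probability 30% and exactly one with 4% at target rates. At uninteresting rates these are 19% and 47%. These are chances that a larger size is allowed, not that it is used.

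**The case against.** The bounds are descriptive. Section 10.9 offers them for planning, at 20 participants, and says that no formal hypothesis test will be made. The specified analysis is ORR with a Clopper-Pearson interval by arm and tumor type (10.6.1, 10.10), which is valid at any n. Expansion is optional and takes the totality of data into account. No section proposes carrying a count of 3 to a larger sample. The 14.3% and 21.1% figures arise only if a type stops, its places are reassigned, the sponsor chooses that size and the count stays at 3. All of this stands, and it limits the weight of the point.

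A reader might go further in ways that the documents do not support:

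- That Table 8 is wrong. It reproduces at its stated size.
- That no count works anywhere from 22 to 25. At n=25 this depends on the futility rule. The rule counts confirmed and unconfirmed responses, while the endpoint counts confirmed responses only, so the true value lies between the two calculations. For a count of 4 that is 72.8–76.6% power, which straddles 75%.
- That the trial will operate at a 14–21% false-claim rate. The plan leaves the count unstated; it does not adopt 3.

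What remains is that the only written NSCLC/CRPC count misses the stated bound at sizes the plan permits, and nothing replaces it.

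**Conclusion.** The point holds as a moderate issue limited to the claim rule for NSCLC and CRPC. The plan permits n=21–40 per type and arm, but gives counts and probabilities only for n=20. With the Stage 1 futility rule, a count of 3 exceeds 8% from n=22 onward. No count meets both bounds at n=22–24 under either calculation; n=21 fails only without the futility rule, and n=25 only with it. CRC is not affected with the futility rule applied. ORR estimates and exact intervals are not affected.

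The calculation treats Stage 1 responses and final responses as the same variable, as the match to Table 8 suggests the plan did. Because unconfirmed responses can open Stage 2, actual probabilities lie between the two columns (for example, 14.3–18.8% for a count of 3 at n=30).

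**What to change.** Before Stage 2 opens, add size-specific minimum counts and their probabilities to Table 8. For NSCLC/CRPC: 3 at n=20–21, 4 at n=22–32, 5 at n=33–40. Keep 2 for CRC. With the futility rule, the NSCLC/CRPC false-claim probability is then at most 7.6%, and power is 75–84% at n=26–40. Two departures must be disclosed, or those sizes excluded: power of 65–73% at n=22–25 with the futility rule, and an 8.5% false-claim probability at n=21 for an Arm B type expanded irrespective of its own responses. A count of 4 at n=21 would remove the second but cut power to 61%. The change to 5 at n=33 is chosen because a count of 4 there gives 8.1% without the futility rule. The cost is a few table rows and one disclosure, with no added participants.

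Alternatively, if the flexibility is not needed, fix Stage 2 at exactly 10 per cleared type, so that 30, 20 or 10 more enter each arm as three, two or one types clear. Table 8 then applies as stated. The synopsis (number of participants and treatment groups), Sections 5.1, 5.1.4, 5.2 and 10.7 and Figure 1 would have to be reconciled with Section 10.9. The cost is less precision for the remaining types when a type stops.

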### 10.6.1 Statistical Methods for Efficacy Analysis

ORR will be estimated using an exact method based on the binomial distribution together with its 95% confidence interval (Clopper-Pearson interval).

Methods for the secondary and exploratory efficacy analyses as well as the comparison between the two arms will be documented in the sSAP.

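### Does Table 9's use of 90% and 80% intervals undercut the planned 95% interval for objective response?

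*Combined protocol and SAP*

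**What the plan says.** Sections 10.1 and 10.6.1 set the primary efficacy analysis: "ORR will be estimated using an exact method based on the binomial distribution together with its 95% confidence interval (Clopper-Pearson interval"). Section 10.10 has efficacy analysed by arm within each tumor type, and section 10.9 gives the cell size: "The total sample size is 60 participants per arm (20 per each tumor type in an arm").

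For precision, section 10.9 says "Table 9 shows the hypothetical ORR estimates and the CI (Clopper-Pearson interval) based on sample size of 20 per tumor type". The table's two interval columns are headed 90% and 80%; there is no 95% column. Two remarks interpret it. The first is that "even an observed response rate as high as 30% (6 out of 20) could be coming from a true signal as low as 14" percent; the second is "A higher observed responses rate such as 8 out of 20 would be more indicative of a true response rate above 20" percent. Neither names a confidence level.

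The decision rule stands apart from the intervals. For planning, "true objective response rates of <1% for MSS CRC and 5% for PDL1-refractory NCSLC and advanced prostate are not considered clinically meaningful". Table 8 has a column headed "Minimum Responses that ORR is claimed as clinical meaningful", set at 2 of 20 for colorectal cancer and 3 of 20 for lung and prostate cancer. It prints false-claim probabilities of 1% and 7%, and probabilities of a correct claim of 77% and 76%. The section also rules out a formal hypothesis test.

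**The concern.** A precision table should show the interval that the analysis will report. Here the analysis is fixed at 95% and the illustration stops at 90%, with no reason given. A reader who relies on Table 9 will expect narrower intervals than the study report will contain. At 95% no row of the table has a lower limit above 20%, so the 8/20 remark appears to lose its support, and 6/20 reaches lower than the text says.

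The claim rule seems to add a second conflict. For lung and prostate cancer, 3/20 would be called clinically meaningful beside a reported interval that still contains 5%, the rate labelled not meaningful. Response rate is the endpoint used for decisions (section 5.4.1.1), and six cells of 20 will be reported this way, so a misleading statement of precision could affect how each is read.

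**Working it through.** **Inputs.** n = 20 per cell; Clopper-Pearson limits; levels of 95% (10.6.1) and 90% and 80% (Table 9); claim thresholds of 2/20 and 3/20 (Table 8). The futility rule in 10.7 is that with at least 1 response in the first 10, "this tumor type may be expanded to enroll at least 10 additional participants in Stage 2". The check takes exactly 10 more.

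**Step 1: reproduce Table 9 and add the planned level.** The Clopper-Pearson lower limit solves P(X ≥ x | n, p) = α/2, and the upper limit solves P(X ≤ x | n, p) = α/2. As beta quantiles these are B(α/2; x, n−x+1) and B(1−α/2; x+1, n−x).

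| Responses | 95% | 90% | 80% |
|---|---|---|---|
| 2/20 | 1.2, 31.7 | 1.8, 28.3 | 2.7, 24.5 |
| 3/20 | 3.2, 37.9 | 4.2, 34.4 | 5.6, 30.4 |
| 4/20 | 5.7, 43.7 | 7.1, 40.1 | 9.0, 36.1 |
| 5/20 | 8.7, 49.1 | 10.4, 45.6 | 12.7, 41.5 |
| 6/20 | 11.9, 54.3 | 14.0, 50.8 | 16.6, 46.7 |
| 7/20 | 15.4, 59.2 | 17.7, 55.8 | 20.7, 51.8 |
| 8/20 | 19.1, 63.9 | 21.7, 60.6 | 24.9, 56.7 |
| 9/20 (not in Table 9) | 23.1, 68.5 | 25.9, 65.3 | 29.3, 61.5 |

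The 90% and 80% columns match Table 9 to the printed decimal. The 14% in the text is the 90% lower limit for 6/20.

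**Step 2: reproduce Table 8.** With r the claim threshold, X1 the responses in the first 10 and X2 those in the second 10:

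P(claim) = P(X ≥ r | 20, p) − P(X1 = 0) × P(X2 ≥ r | 10, p)

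- Colorectal, p = 1%, r = 2: 0.0169 − 0.9044 × 0.0043 = 1.3% (printed 1%)
- Colorectal, p = 16%, r = 2: 0.8529 − 0.1749 × 0.4920 = 76.7% (printed 77%)
- Lung and prostate, p = 5%, r = 3: 0.0755 − 0.5987 × 0.0115 = 6.9% (printed 7%)
- Lung and prostate, p = 20%, r = 3: 0.7939 − 0.1074 × 0.3222 = 75.9% (printed 76%)

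No confidence limit enters these figures.

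**Step 3: test each remark at 95%.** A lower limit excludes a rate p when P(X ≥ x | p) is below α/2, which is 2.5%, 5% and 10% for the three levels.

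- *6/20 and 14%.* P(X ≥ 6 | 14%) = 5.1%, above 2.5%, so 14% lies inside the 95% interval. The remark that 6/20 could come from such a rate is true at 95%, where the interval reaches down to 11.9%.
- *8/20 and 20%.* P(X ≥ 8 | 20%) = 3.2%, so 20% is excluded at 90% and not at 95%. The shortfall is 20.0 − 19.1 = 0.9 percentage points, with a point estimate of 40%. The first count to exclude 20% at 95% is 9/20 (23.1%).
- *3/20 and 5%.* P(X ≥ 3 | 5%) = 7.5%, so 5% is included at 95% and at 90%, and excluded only at 80%. The printed 90% limit of 4.2% already shows this.
- *2/20 and 1%.* P(X ≥ 2 | 1%) = 1.7%, so the colorectal rule agrees with the 95% interval (lower limit 1.2%).

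**Step 4: the chance of excluding 5% at 95%.** This needs 4/20. At a true rate of 20%, P(X ≥ 4) = 0.79392 − 0.20536 = 0.58856. Subtracting the paths stopped at stage 1, 0.10737 × 0.12087 = 0.01298, gives 57.6%, against 75.9% for a claim. The plan never presents its 76% as the chance of excluding 5%.

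**The case for a change.** The strongest argument for acting is that the correction is cheap and best made before data are seen. Response rate drives decisions, the trial is open-label, and section 10.7 allows data to be examined continuously. An unexplained difference in level might leave room to choose an interval later. A 95% column, a 9/20 row and a note that 3/20 does not exclude 5% would cost a few lines.

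Part of this stands. The levels do differ, the text does not name the level behind its two remarks, and a 95% column would have been the natural choice. The worry about a later choice does not stand, because sections 10.1 and 10.6.1 both fix the reported interval at 95% and Table 9 does not compete with them.

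The 3/20 point is not produced by the choice of 90% over 95%. A count rule with about 7% one-sided error will not generally line up with an interval that leaves 2.5% in each tail. That is a trade-off open to a phase 2 screening design, and Table 8 discloses it. Adding an 80% interval to 10.6.1 so that interval and rule agree would be a matter of taste. Rewriting the 8/20 remark around 9/20 would turn a loose comparison into an exclusion threshold that the plan does not use.

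**Conclusion.** No change is needed. The mismatch is one of presentation in an illustrative table. At the planned level the lower limit moves from 14.0% to 11.9% for 6/20 and from 21.7% to 19.1% for 8/20. The 6/20 warning becomes stronger, and 8/20 remains more suggestive of a rate above 20% than 6/20 is. For 3/20 the planned interval contains 5%, as the printed 90% interval already does, so a reader of Table 9 is not misled on that point.

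Followed as written, the plan reports the correct 95% interval in every cell and applies the same futility rule, claim thresholds and sample size. An added column would alter no result or decision.

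This rests on three readings: exactly 20 participants per cell (the plan allows more than 10 in stage 2), the futility rule applied as a binding stop (the wording is permissive, but Table 8 reproduces on that basis), and the 1% and 5% rates taken as planning references, since no test is planned. Anyone writing up a claim at exactly 3/20 can state beside it that the 95% interval includes 5%.
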